2 PROTOCOL SUMMARY

Protocol Title:	Deucravacitinib for the Treatment of Palmoplantar Pustulosis
Background:	
Palmoplantar pustulosis (PPP) is a chronic, orphan disease associated with significant morbidity. Previously considered a subtype of psoriasis, important differences identified in the immune dysregulation between psoriasis and PPP suggest they are distinct entities. Because of these important differences in the inflammatory profile, patients with PPP have an unpredictable and frequently inadequate response to therapies that are highly effective for plaque psoriasis. There are currently no FDA approved treatments specifically for PPP and few prospective trials have been performed specifically in these patients.
 
Deucravacitinib is a novel, selective TYK2 inhibitor with a unique mechanism of action compared to other Janus kinase (JAK) inhibitors. Deucravacitinib binds to the regulatory pseudokinase domain of TYK2 rather than to the active adenosine triphosphate-binding site in the catalytic domain of TYK2. Binding by deucravacitinib allosterically locks the regulatory domain, inhibiting the interaction with the catalytic domain. This blocks activation of TYK2, inhibiting TYK-2 mediated signaling of by cytokines involved in the psoriasis pathogenesis including IL-23, IL-12 and Type 1 interferon. Deucravacitinib has previously demonstrated efficacy in Phase II/III trials of plaque psoriasis. Given that IL-12 and IL-23 are involved in the pathogenesis of both plaque psoriasis and palmoplantar pustulosis, deucravacitinib is an exciting potential novel therapy for this orphan disease.

Study Descriptions:	A prospective, single-arm, open-label trial of deucravacitinib 6 mg daily in patients with PPP. All participants will receive deucravacitinib 6 mg daily for 24 weeks, with study visits every 4 weeks.
Objectives:	
1. Evaluate the efficacy of deucravacitinib in adults with PPP2. Evaluate the impact of deucravacitinib on quality of life in adults with PPP3. Evaluate the safety of deucravacitinib
Primary Endpoint:	
• Proportion of participants who achieve a ppPASI-50 response, or at least 50% improvement in ppPASI score, at 16 weeks
Secondary Endpoints:	
• Proportion of participants who achieve at least 50% improvement in the palmoplantar pustular psoriasis area and severity index (ppPASI-50) at 24 weeks• Frequency of participants with adverse events• Change from baseline in the Dermatology Quality of Life Index• Change from baseline in ppPASI• Percentage of patients who achieved a static Physician's Global Assessment score of 0/1• Change from baseline in the EQ-5D VAS score• Change from baseline in itch VAS• Change from baseline in pain VAS
Inclusion Criteria:	
• Adults aged 18 years of age and older• Dermatologist confirmed diagnosis of PPP for at least 6 months• Moderate-severe PPP, defined as a ppPASI ≥ 12• Inadequate response to topical therapy and a candidate for systemic or phototherapy• Willing to discontinue current topical and/or systemic PPP treatments, except for OTC emollients• Willing to use acceptable contraception methods or maintain abstinence for the duration of the study
Exclusion Criteria:	
• Participants with other immune-mediated conditions requiring concurrent systemic immunosuppressant treatments• Current/recent administration of PPP-specific medications including:
○ Rituximab within 6 months of the baseline visit

Mass General Brigham Institutional Review Board
Intervention/Interaction Detailed Protocol

	
 ○ Biologics within 12 weeks of baseline visit ○ Systemic steroids, oral immunosuppressants (azathioprine, cyclosporine, methotrexate, mycophenolate mofetil, tacrolimus), oral retinoids (acitretin, isotretinoin), apremilast, or dapsone within 4 weeks of baseline visit ○ Phototherapy within 4 weeks of baseline visit ○ Prescription topical medications (including calcineurin inhibitors, crisaborole, retinoids, steroids, tar, vitamin D analogs) within 2 weeks of baseline visit ● History of active infection and/or febrile illness within 7 days; or infection requiring antibiotic treatment within 30 days; or serious infection requiring hospitalization and/or IV antibiotics within 90 days ● Evidence of other infection including: 
 ○ Active or untreated latent tuberculosis, defined as radiographic or laboratory evidence of active TB or positive quantiferon or PPD, unless the subject has completed the recommended treatment ○ Human immunodeficiency virus infection (positive HIV antibody) ○ Active hepatitis B ○ Active hepatitis C ● Evidence of clinically significant laboratory abnormality including: 
 ○ Absolute WBC count < 3000/mm³ ○ Platelet count < 100,000/mm³ ○ Hemoglobin < 9.0 g/dl ○ ALT or AST > 3 times the upper limit of normal ● History of cancer within the past 5 years, excluding treated non-melanoma skin cancer (basal cell carcinoma, squamous cell carcinoma) ● Other uncontrolled chronic medical condition that may interfere with a patient's ability to participate in the clinical trial ● Major surgery within 4 weeks of baseline visit ● Receipt of live vaccine within 8 weeks of baseline visit ● Pregnant or breastfeeding individuals ● Inability to comply with any of the study procedures ● Individuals who are incarcerated or compulsory detained
Sample Size:	A modified Simon's two-stage design will be used to maximize the safety and efficiency of this clinical trial in an orphan disease. In the first stage, 8 patients will be accrued. If 2 or fewer patients achieve a ppPASI-50 in these 8 patients, the study will be stopped. Otherwise, 10 additional patients will be accrued for a total of 18.
Analysis Plan:	Descriptive statistics will be used to characterize the study population, including demographics, disease characteristics and previous treatments. For the primary outcome, the percentage of participants who achieve a ppPASI-50 response, or at least 50% improvement in ppPASI score, at 16 weeks, the response rate with a 95% CI will be calculated. For all secondary endpoints, summary and descriptive statistics will be used as appropriate, including number of observations, calculation of mean/median, standard deviation range and 95% confidence intervals.

3 BACKGROUND AND SIGNIFICANCE

Palmoplantar pustulosis (PPP) is a limited form of pustular psoriasis characterized by persistent, sterile macroscopic pustules on the palms and/or soles¹ and associated with significant morbidity. PPP is a rare disease with an estimated one-year prevalence between 0.005% - 0.12%.¹⁻³ It has been reported as a solitary disease and in patients with a history of plaque psoriasis.

Previously considered a subtype of psoriasis, important differences identified in the immune dysregulation between psoriasis and PPP suggest they are distinct entities. Genetic susceptibility to plaque psoriasis is polygenic, with 63 genes accounting for 28% of the heritability.⁴ Genes associated with antigen presentation, keratinocyte proliferation and differentiation, and production of pro-inflammatory cytokines in TH-17 cells all play an important role.⁵ A different genetic profile has been associated with pustular psoriasis. Coding mutations in IL36RN, CARD14, AP1S3, SERPINA3, and MPO that affect IL-1 and IL-36 signaling have been associated with the clinical spectrum of pustular psoriasis.⁵ Additionally, the inflammatory profiles between plaque psoriasis and pustular psoriasis have key differences. Plaque psoriasis is a T-cell mediated disease, largely driven by the IL-23/Th-17 pathway.⁶ Overexpression of IL-23 by activated dendritic cells stimulates Th-17 differentiation, cell survival, and proliferation, resulting in the production of additional cytokines: IL-17A, IL-22, and INF- γ . These cytokines cause the activation and hyperproliferation of keratinocytes, resulting in the characteristic plaque development.⁷ In PPP IL-8, IL-36 gamma and IL-36Ra have been found to be overexpressed in lesional skin.⁸ The IL-17A pathway is thought to play a more important role in PPP compared to plaque psoriasis.⁹

Because of these important difference in the inflammatory profile, patients with PPP have an unpredictable and frequently inadequate response to therapies that are highly effective for plaque psoriasis. There are currently no FDA approved treatments for PPP, and therefore, in the current standard practice, much of the information regarding treatment is adapted from plaque psoriasis. A Cochrane Review published in 2020 concluded that evidence is lacking for the efficacy of all chronic PPP treatments.¹⁰ The few randomized control trials that have been performed are small and sometimes also include palmar plantar psoriasis, which complicated interpretation of the results. We recently published a retrospective cohort of 197 PPP patients from across the United States where more than 20 different treatments were tried in patients with PPP and a median of 6 visits per year of follow-up, suggesting a lack of effective treatments to control this chronic disease.¹¹

Case reports suggest that off-label use of Janus kinase (JAK) inhibitors may be effective in the treatment of PPP. The JAK kinase family consists of 4 intracellular tyrosine kinases: JAK1, JAK2, JAK3 and TYK2.¹² JAK activation occurs via binding of a cytokine to JAK associated type I and II receptors. Activated JAKs initiate transphosphorylation, initiating the recruitment of signal transducers and activators of transcription (STAT) proteins. The JAK-STAT pathway mediates signaling downstream of receptors for Type I and Type II cytokines, including IL-6, IL-10, IL-12, IL-22, IL-23, interferon (IFN)- α , IFN- β , and IFN- γ , important cytokines in a variety of chronic inflammatory diseases.¹³ There are reports of successful treatment of PPP, with both tofacitinib, an oral JAK1 and JAK3 inhibitor¹⁴⁻¹⁷ and also baricitinib, an oral JAK1 and JAK2 inhibitor.¹⁸

Deucravacitinib is a novel, selective TYK2 inhibitor with a unique mechanism of action from other Janus kinase (JAK) inhibitors. Deucravacitinib binds to the regulatory pseudokinase domain of TYK2 rather than to the active adenosine triphosphate-binding site in the catalytic domain of TYK2, where other JAK

inhibitors bind. Binding by deucravacitinib allosterically locks the regulatory domain, inhibiting the interaction with the catalytic domain. This blocks activation of TYK2, inhibiting TYK-2 mediated signaling of by cytokines involved in the psoriasis pathogenesis including IL-23, IL-12 and Type 1 interferon.¹⁹

Deucravacitinib has previously demonstrated efficacy in phase II and phase III trials of plaque psoriasis. In the Phase 2 randomized, double-blind, parallel-group, clinical study of increasing doses deucravacitinib placebo in subjects with moderate to severe PsO. The Deucravacitinib treatment demonstrated a dose-dependent improvement in PASI 75, with the 3 highest doses of 3 mg BID, 6 mg BID, and 12 mg QD showing similar responses of 68.9%, 66.7%, and 75.0%, respectively, versus placebo response of 6.7%.²⁰ In the 2 Phase III studies in psoriasis (NCT03624127, NCT03611751), deucravacitinib demonstrated robust and statistically significant efficacy compared with placebo and apremilast, with clinically meaningful improvements in multiple clinical and quality of life parameters in a broad population of patients with moderate-to-severe psoriasis naïve to prior treatment or treatment experienced.²¹ Given that IL-12 and IL-23 are involved in the pathogenesis of both plaque psoriasis and palmoplantar pustulosis, deucravacitinib is an exciting potential novel therapy for an orphan disease and further investigation is warranted.

4 OBJECTIVES & ENDPOINTS

4.1 Objectives

- Evaluate the efficacy of deucravacitinib in adults with PPP
- Evaluate the impact of deucravacitinib on quality of life in adults with PPP
- Evaluate the safety of deucravacitinib

4.2 Primary Endpoint

- Proportion of participants who achieve at least 50% improvement in the palmoplantar pustular psoriasis area and severity index (ppPASI-50) at 16 weeks.
- **Hypothesis:** 50% of patients treated with deucravacitinib 6 mg once daily for 16 weeks will achieve at least 50% improvement in disease severity (ppPASI-50)

4.3 Secondary Endpoints

- Frequency of patients with adverse events at week 16 & 24
- Change from baseline in the Dermatology Quality of Life Index (DLQI) at week 16 & 24
- Change from baseline in ppPASI at week 16 & 24
- Percentage of patients who achieved a Physician's Global Assessment score of 0 or 1 at week 16 & 24
- Change from baseline in the EQ-5D VAS score at week 16 & 24
- Change from baseline in itch VAS at week 16 and 24 weeks
- Change from baseline in pain VAS at week 16 and 24 weeks
- Proportion of participants who achieve at least 50% improvement in the palmoplantar pustular psoriasis area and severity index (ppPASI-50) at 24 weeks

5 GENERAL DESCRIPTION OF STUDY DESIGN

This is a prospective, single-arm, open-label trial of deucravacitinib 6mg once daily in patients with PPP. All participants will receive deucravacitinib 6 mg once daily for 24 weeks, with study visits every 4 weeks. The study schema can be found in Appendix A.

6 SUBJECT SELECTION & ELIGIBILITY

6.1 Recruitment Strategies

Male and female participants representing all ethnic groups and racial categories will be recruited for this study. Recruitment strategies may include:

- Referrals from study site-specific physicians and physicians in the surrounding communities
- Targeted Research Announcements
- Institutional and lab-specific clinical research websites
- Advertisements on the internet, including clinicaltrials.gov and in-print media advertisements
- Interactions with patient and physician organizations in the local and national dermatology community

6.2 Inclusion Criteria

- Adults aged 18 years of age and older
- Dermatologist confirmed diagnosis of PPP for at least 6 months
- Moderate-severe PPP, defined as a pPASI ≥ 12
- Inadequate response to topical therapy and a candidate for systemic or phototherapy
- Willing to discontinue current topical and/or systemic PPP treatments, except for OTC emollients
- Willing to use acceptable contraception methods or maintain abstinence for the duration of the study

6.3 Exclusion Criteria

- Participants with other immune-mediated conditions requiring concurrent systemic immunosuppressant treatments
- Current/recent administration of PPP-specific medications including:
 - Rituximab within 6 months of the baseline visit
 - Biologics (including adalimumab, anakinra, brodalumab, certolizumab, etanercept, golimumab, guselkumab, infliximab, ixekizumab, rizankizumab, secukinumab, spesolimab, tildrakizumab, ustekinumab) within 12 weeks of baseline visit.
 - Systemic steroids, oral immunosuppressants (azathioprine, cyclosporine, methotrexate, mycophenolate mofetil, tacrolimus), oral retinoids (acitretin, isotretinoin), apremilast, or dapsone within 4 weeks of baseline visit
 - Phototherapy within 4 weeks of baseline visit
 - Prescription topical medications (including calcineurin inhibitors, crisaborole, retinoids, steroids, tar, vitamin D analogs) within 2 weeks of baseline visit

- History of active infection and/or febrile illness within 7 days; or infection requiring antibiotic treatment within 30 days; or serious infection requiring hospitalization and/or IV antibiotics within 90 days
- Evidence of other infection including:
 - Active or untreated latent tuberculosis, defined as radiographic or laboratory evidence of active TB or positive quantiferon or PPD, unless the subject has completed the recommended treatment)
 - human immunodeficiency virus infection (positive HIV antibody)
 - Active hepatitis B
 - Active Hepatitis C
- Evidence of clinically significant laboratory abnormality including:
 - Absolute WBC count < 3000/mm³
 - Platelet count < 100,000/mm³
 - Hemoglobin < 9.0 g/dl
 - ALT or AST > 3 times the upper limit of normal
- History of cancer within the past 5 years, excluding treated non-melanoma skin cancer (basal cell carcinoma, squamous cell carcinoma)
- Other uncontrolled chronic medical condition that may interfere with a patient's ability to participate in the clinical trial
- Major surgery within 4 weeks of baseline visit
- Receipt of live vaccine within 8 weeks of baseline visit
- Pregnant or breastfeeding individuals
- Inability to comply with any of the study procedures
- Individuals who are incarcerated or compulsory detained

7 SUBJECT ENROLLMENT & INFORMED CONSENT

7.1 Enrollment

- Subjects will be pre-screen by study staff over the telephone.
- Those who meet the telephone screening criteria will be brought to clinic for a screening visit.
- Before any study procedures are performed, subjects will have the details of the study described to them, and they will be given a written informed consent document to read. Then, if subjects consent to participate in the study, they will indicate their consent by signing and dating the informed consent document in the presence of study personnel.
- After consent has been obtained, the participant will participate in a screening visit to determine eligibility including review of inclusion/exclusion criteria, physical exam with disease severity measures and laboratory evaluation as detailed in Appendix B.
- Patients will be notified of eligibility by phone when all results are available and baseline visit will be scheduled.

7.2 Informed Consent

- We will use the REDCap eConsent feature to collect digital signatures, during the in person Informed Consent Process the investigators will:
 - Provide a paper copy of the consent form and written information about the study in the language in which the subject is most proficient prior to clinical study participation.

The language must be non-technical and easily understood. Interpreters will be available (in person or telephone) for all participation whose preferred language is not English.

- Allow time necessary for subject or subject's legally acceptable representative to inquire about the details of the study.
- Obtain an electronic signature of the informed consent and dated by the subject or the subject's legally acceptable representative and by the person who conducted the informed consent discussion. Once all e-signatures are collected, the patient will receive a copy of the fully signed consent via email.
- If informed consent is initially given by a subject's legally acceptable representative or legal guardian, and the subject subsequently becomes capable of making and communicating their informed consent during the study, then consent must additionally be obtained from the subject.
- Revise the informed consent whenever important new information becomes available that is relevant to the subject's consent. The investigator, or a person designated by the investigator, should fully inform the subject or the subject's legally acceptable representative or legal guardian, of all pertinent aspects of the study and of any new information relevant to the subject's willingness to continue participation in the study. This communication should be documented.
- The rights, safety, and well-being of the study subjects are the most important considerations and should prevail over interests of science and society.

7.3 Ethical Considerations

- This study will be conducted under the ethical principles that have their origin in the Declaration of Helsinki and in accordance with Good Clinical Practice. In accordance with Good Clinical Practice (GCP), as defined by the International Conference on Harmonization (ICH), WHO and any local directives.
- The protocol, any amendments, and the subject informed consent will receive Institutional Review Board/Independent Ethics Committee (IRB/IEC) approval/favorable opinion before initiation of the study, with personnel who are qualified by education, training, and experience to perform their respective tasks and that the study will not use the services of study personnel for whom sanctions have been invoked or where there has been scientific misconduct or fraud.

8 STUDY ASSESSMENTS & PROCEDURES

8.1 Study Drug

- **Investigational Product (IP):** All study participants will receive deucravacitinib 6mg once daily for a maximum of 24 weeks while enrolled in the study.
- **Storage:** The IP will be stored in a secure area in accordance with the package insert. If concerns regarding the quality or appearance of the study drug arise, the study drug should not be dispensed and BMS should be contacted immediately. A current disposition record of study drug (supplied by BMS) will be maintained at each study site where study drug is inventoried and dispensed.
- **Blinding/Unblinding:** N/A
- **Medication Compliance:** At each study visit compliance with study drug will be reinforced. Diaries will be used to assist subjects in maintaining an accurate assessment of daily pill intake. Subject diaries and returned pill bottles will be required to be returned at every visit.

- **Disposal:** Disposal of unused medication will occur according to applicable regulations, guidelines, and institutional procedures.

8.2 Study Events

At the initial screening visit, after informed consent is obtained, eligibility will be determined through review of inclusion/exclusion criteria and physical exam with determination of disease severity measures. If the patient is deemed eligible to participate, demographic and medical history information will be collected and laboratory evaluation, including CBC, CMP, CPK, triglycerides, HIV test, Quantiferon TB-Gold, Hep B surface antigen, Hep C antibody and urine pregnancy test (as applicable) will be performed. Any labs (except urine pregnancy test) checked in the 90 days prior to the screening visit, as a part of routine clinical care, can be used as a part of the screening labs.

All patients who meet all study eligibility criteria will be scheduled for a baseline study visit within 2 weeks of the screening visit. All study participants will receive deucravacitinib 6 mg once daily for 24 weeks or until participation from the trial is discontinued. Participants will be evaluated with clinical instruments (ppPASI, PGA, DLQI, EQ5D-5L, VAS-itch, VAS-pain) and clinical photographs every 4 weeks for the duration of the study. Additionally, safety assessment of new symptoms/side effects will be asked at every visit and safety labs will be performed at week 16 and week 24. **Please see the Time and Events Schedule (Appendix B) for full details.**

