15 APPENDICES

15.1 Appendix A – Study Scheme

15.2 Appendix B – Study Assessments & Procedures

Visit	1 Screening	2 Baseline	3 Week 4	4 Week 8	5 Week 12	6 Week 16	7 Week 20	8 (EOS) Week 24	Early Termination
Informed consent	X								
Inclusion/exclusion criteria	X								
Medical history	X								
Prior/concurrent medications	X	X	X	X	X	X	X	X	X
New symptoms/side effects		X	X	X	X	X	X	X	X
Dispense study medication		X	X	X	X	X	X		
Assess medication compliance			X	X	X	X	X	X	X
Assessments									
Vital signs		X				X		X	X
Physical exam		X				X		X	X
ppPASI		X	X	X	X	X	X	X	X
PGA		X	X	X	X	X	X	X	X
DLQI		X	X	X	X	X	X	X	X
EQ-5D-5L		X	X	X	X	X	X	X	X
VAS-itch		X	X	X	X	X	X	X	X
VAS-pain		X	X	X	X	X	X	X	X
Photographs (Optional)		X	X	X	X	X	X	X	X
Laboratory Studies									
Urine pregnancy test	X								
CBC, CMP	X					X		X	X
HIV Test	X								
CPK	X					X		X	X
Triglycerides	X					X		X	X
Hep C antibody	X								
Hep B surface antigen	X								
QuantiFERON GOLD TB screen	X								

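### The only scheduled pregnancy test is at Screening: none before first dispensing, up to 14 days later, and none during 168 days of dosing

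*Combined protocol and SAP*

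**What the plan says.** Section 8.2 lists the screening laboratory tests, closing with "Hep C antibody and urine pregnancy test (as applicable) will be performed". The same section lets routine-care results from the 90 days before Screening stand in for the other laboratory tests, but not for this one, so the Screening pregnancy test must be current.

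In Appendix B the row "Urine pregnancy test" has one mark, under Screening. The row "Inclusion/exclusion criteria" is also marked at Screening only. The row "Dispense study medication" is marked at Baseline and Weeks 4, 8, 12, 16 and 20.

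On the order of events, section 7.1 states: "Patients will be notified of eligibility by phone when all results are available and baseline visit will be scheduled". Section 8.2 adds that patients who meet all the criteria "will be scheduled for a baseline study visit within 2 weeks of the screening visit", and that "All study participants will receive deucravacitinib 6 mg once daily for 24 weeks". During treatment, "safety labs will be performed at week 16 and week 24". Section 8.4 gives the content of those laboratory tests as blood count, metabolic panel, creatine phosphokinase and triglycerides.

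Pregnancy is an exclusion (6.3) and a mandatory reason to stop the drug (8.5). Section 12.5 sets out permanent discontinuation and reporting once a pregnancy comes to light. Section 6.2 requires willingness to use contraception or remain abstinent.

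**The concern.** The protocol treats pregnancy as a bar both to starting and to continuing the drug. Section 9.1 gives the reason: human reproductive risk has not been fully assessed, and the drug is not to be given in pregnancy. Both rules depend on someone knowing that the participant is pregnant. At first dispensing, the exclusion rests on a test that may be two weeks old. During treatment, the stopping rule in 12.5 acts on discovery, and no scheduled test looks for a pregnancy. A site that follows the schedule exactly could start or continue dosing in an undetected pregnancy.

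**Working it through.** The check is a row-by-row reading of Appendix B against the text, plus simple calendar arithmetic. No sample-size, power or error-rate formula is involved.

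**Schedule, from Appendix B**

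| Visit | Pregnancy test | Drug dispensed | Laboratory tests marked |
|---|---|---|---|
| Screening | Yes | No | Full screening panel |
| Baseline | No | Yes (first) | None |
| Weeks 4, 8, 12 | No | Yes | None |
| Week 16 | No | Yes | CBC, CMP, CPK, triglycerides |
| Week 20 | No | Yes | None |
| Week 24 | No | No | CBC, CMP, CPK, triglycerides |
| Early Termination | No | No | CBC, CMP, CPK, triglycerides |

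The test appears in 1 of 9 visit columns. None of the 6 dispensing visits has a same-day test. Section 8.4 places a set of laboratory tests at baseline, whereas Appendix B places the pre-treatment set at Screening; on either reading no pregnancy test falls at Baseline. The text of 8.2 agrees with the table, so the single mark is not a fault of table extraction.

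**Intervals without a test, from the durations in 8.2**

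- Screening to first dispensing: 2 × 7 = 14 days at most under the scheduling rule.
- Dosing period: 24 × 7 = 168 days.
- Screening to Week 24: 14 + 168 = 182 days at most.

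**Effect of three possible schedules**

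For each option, the upper limit on added tests is the number per participant times 18 (full enrolment) or times 8 (trial stopped after stage 1), as if every participant were of childbearing potential.

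| Option | Added tests per participant | Longest untested stretch, Baseline to Week 24 | Upper limit, 18 participants | Upper limit, 8 participants |
|---|---|---|---|---|
| Baseline only | 1 | 24 × 7 = 168 days | 1 × 18 = 18 | 1 × 8 = 8 |
| Baseline, Week 16, Week 24/Early Termination | 3 | 16 × 7 = 112 days (then 8 × 7 = 56) | 3 × 18 = 54 | 3 × 8 = 24 |
| Baseline, Weeks 4, 8, 12, 16 and 20, Week 24/Early Termination | 7 | 4 × 7 = 28 days | 7 × 18 = 126 | 7 × 8 = 56 |

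With any of the three, the gap between the last test and first dispensing falls from up to 14 days to 0.

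**The case against.** The schedule itself is not in dispute. The case on the other side is about weight.

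- **The two gaps are not equally strong.** The first-dose gap concerns a definite exclusion criterion and closes with one mark in the table. The documents set no on-treatment testing interval that the plan fails, so repeat testing is a matter of judgement. This stands in part: the Baseline test is the firmest part of the recommendation, and the frequency of repeats is properly left to the sponsor. It does not justify having no repeat at all.
- **The minimum option is modest.** It leaves a stretch of 112 days, and its last test comes after dispensing has ended, so it would inform follow-up under 12.5 but prevent almost no exposure. That is correct, and it is the argument for the fuller option. No schedule removes the possibility of an undetected pregnancy; repeat tests shorten how long one can go unnoticed.
- **Eligibility may not be closed at Screening.** Several criteria in 6.3 (washouts, surgery, live vaccine) are timed to the baseline visit, and Baseline includes a physical examination and a medication review. However, 8.2 sends only patients who already meet all criteria to Baseline, and the criteria check is marked only at Screening. Even if eligibility is reviewed again informally, no pregnancy test is scheduled for that review.
- **Other controls exist.** These are contraception or abstinence, symptom questions and medication review at visits, and physical examinations at Baseline, Week 16, Week 24 and Early Termination. Nothing forbids an unscheduled test. All of these reduce the risk; none is a scheduled test.
- **Durations are not risks.** This is true, and no pregnancy count is claimed here.

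**Conclusion.** The concern holds. The protocol schedules one urine pregnancy test, at Screening. It leaves up to 14 days before first dispensing and then 168 days of dosing without another, up to 182 days in all. This is a participant-safety gap that should be closed; it does not threaten the efficacy analysis.

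The conclusion rests on the following:

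- The 14 and 182 days assume that Baseline takes place within the 2-week rule. The protocol gives no re-test rule if it slips, so the gap could be longer in practice.
- The 168 days is the planned maximum and is shorter for anyone who stops early.
- The number of participants of childbearing potential is not given (at most 18), nor is a pregnancy rate, so the expected number of affected participants is unknown.
- The point is limited to the schedule of tests in the protocol. It makes no claim about instructions given to participants elsewhere.

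**What to change.** For participants of childbearing potential, amend section 8.2 and the pregnancy-test row of Appendix B as follows:

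1. Add a urine pregnancy test at Baseline and require a negative result before the first dispensing.
2. Repeat the test during treatment at visits already planned. As a minimum, do it alongside the safety laboratory tests at Week 16 and at Week 24 or Early Termination. A fuller option is a test before each dispensing at Weeks 4, 8, 12, 16 and 20, plus Week 24 or Early Termination. The sponsor should choose the frequency.

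The cost is a few marks in one table row, a matching line in 8.2, and 3 (minimum) or 7 (fuller) added urine tests per participant concerned. No visits are added, and the primary endpoint, type I error and power do not change.
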